8.6.4 Secondary Endpoints

For secondary endpoints, between group comparisons from baseline to week 8 will be performed as described in Section 8.6.1 as follows:

- Seizure response at Week 8 (a percent reduction from baseline in seizure frequency greater than or equal to 50%, see Section 5.7.4) will be analyzed, based on the Efficacy Analysis Set, using logistic regression. The baseline covariate will be the natural logarithm of the baseline seizure frequency (+ 1): observable seizures from the diary will be used for Observable Seizures Subjects and absence seizures from EEG will be used for Absence Seizures Only Subjects. An additional covariate will be included that indicates whether the subject is an Observable Seizures Subject or an Absence Seizures Only Subject.
- Reduction from baseline in frequency of observable seizures will be analyzed, based on the Efficacy Analysis Set, using linear regression. The response variable in the model will be the change in the natural logarithm of the observable seizure frequency (+ 1) from baseline to Week 8 and the baseline covariate will be the natural logarithm of the baseline frequency (+ 1) of observable seizures (see Section 5.7.5). Estimates and 90% confidence intervals of percent reduction in observable seizure frequency will be derived from the model for each treatment group and for the difference between groups.
- Observable seizure response at Week 8 will be analyzed, based on the Efficacy Analysis Set, using logistic regression. Observable seizure frequency will be calculated based on approximately 6 weeks between the end of titration and the week 8 visit. The baseline covariate will be the natural logarithm of the baseline frequency (+ 1) of observable seizures (see Section 5.7.5).
- Reduction from baseline in frequency of absence seizures will be analyzed, based on the Efficacy Analysis Set, using linear regression. The response variable in the model will be

the change in the natural logarithm of the absence seizure frequency (+ 1) from baseline to Week 8 and the baseline covariate will be the natural logarithm of the baseline frequency (+ 1) of absence seizures. Estimates and 90% confidence intervals of percent reduction in absence seizure frequency will be derived from the model for each treatment group and for the difference between groups.

- Absence seizure response at Week 8 will be analyzed, based on the Efficacy Analysis Set, using logistic regression. The baseline covariate will be the natural logarithm of the baseline frequency (+ 1) of absence seizures.
- Change from baseline in each of the 8 CANTAB scores will be analyzed, based on the Efficacy Analysis Set – CANTAB, using GEE with identity link function. The baseline covariate will be the baseline value of the corresponding CANTAB score.
- Change from baseline in 6MWT distance traveled (in meters and percent predicted) will be analyzed, based on the Efficacy Analysis Set – 6MWT, using GEE with identity link function. The baseline covariate will be the baseline value of the corresponding 6MWT measure.
- Since a high proportion of subjects do not experience onset of PED during the 6MWT, onset of PED will be analyzed as a binary indicator for whether PED occurred (yes/no). Onset of paroxysmal exertional dyskinesia (PED) during the 6MWT (yes/no) will be analyzed, based on the Efficacy Analysis Set – 6MWT, using GEE with logistic link function. The baseline covariate will be the baseline value of the indicator for onset of PED.
- Change from baseline in GMFM-88 Total score will be analyzed, based on the Efficacy Analysis Set – GMFM-88, using GEE with identity link function. The baseline covariate will be the baseline value of GMFM-88 Total score.

Missing data will be imputed as specified in Section 7.1.

Each endpoint will be summarized by visit, by treatment group, for subjects while taking UX007, and overall.

The following additional analyses will be performed:

- An analysis will be performed using the Per Protocol Analysis Set for endpoints involving all seizures, and the Per Protocol Analysis Set – Observable Seizures for endpoints involving seizures from the diary only, the Per Protocol Analysis Set – Absence Seizures for endpoints involving seizures from EEG only, and the Per Protocol Analysis Set – CANTAB for the CANTAB endpoints (see Section 6.4).
- For seizure response, an analysis will be performed with seizure frequency at baseline and Week 8 derived for each subject based on subject seizure type at randomization: observable seizures from the diary will be used for Observable Seizures Only Subjects and absence seizures from EEG will be used for Absence Seizures Subjects (see Section 5.6).

- For endpoints involving seizures, an analysis will be performed using the alternative imputation methods described in Section 7.1.
- For endpoints involving observable seizures from the seizure diary, an analysis will be performed using observable seizure frequency at week 8, including titration period, calculated based on seizure diary data collected for approximately 8 weeks from baseline to week 8.

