5.6 Classification of Subjects at Randomization by Seizure Type

Classification of subjects is used to derive the primary efficacy endpoint and to define which subjects are included in secondary endpoint analyses of specific seizure types. At the Randomization Visit, subjects can be classified according to the types of seizures that are recorded on the diary as follows:

- **Observable Seizures Subject:** a subject who meets any of the following:
 - Observable Seizure Frequency (types A, B, C, D, E, F, G, H, I, J, K and L; see Section 5.7.5) greater than or equal to 4 at Randomization
 - Observable Seizure Frequency less than 4 at Randomization and Absence Seizure Frequency less than 4 at Randomization
- **Absence Seizures Subject:** a subject who meets any of the following:
 - has seizure types M, N, O or P (see Section 5.7.5) recorded on the seizure diary during the Baseline Period
 - has absence seizures documented on the Screening EEG
 - Absence Seizure Frequency (see Section 5.7.2) greater than 0 at Randomization

All subjects will either be an Observable Seizures Subject, an Absence Seizures Subject, or both. Since there is potential overlap, the following definitions are used to classify randomized subjects into three mutually exclusive groups:

- **Observable Seizures Only Subject:** a subject who is an Observable Seizures Subject *but not an Absence Seizure Subject*
- **Absence Seizures Only Subject:** a subject who is an Absence Seizures Subject *but not an Observable Seizure Subject*
- **Both Seizures Subject:** a subject who is both an Observable Seizures Subject and an Absence Seizure Subject

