6.4.1 Per Protocol Analysis Set – Observable Seizures

The Per Protocol Analysis Set – Observable Seizures is the subset of subjects in the Efficacy Analysis Set – Observable Seizures who met the following criteria:

- met all inclusion and exclusion criteria at the time of randomization
- have $\geq 80\%$ dosing compliance from baseline to week 8
- have sufficiently complete seizure data: completed at least 28 days of the seizure diary during the 6-week baseline period and again during weeks 3-8 of the double-blind placebo-controlled treatment period

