6.4.2 Per Protocol Analysis Set – Absence Seizures

The Per Protocol Analysis Set – Absence Seizures is the subset of subjects in the Efficacy Analysis Set – Absence Seizures who met the following criteria:

- met all inclusion and exclusion criteria at the time of randomization
- have $\geq 80\%$ dosing compliance from baseline to week 8
- have sufficiently complete seizure data: at least 8 hours evaluable EEG at randomization and again at week 8

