9 PLANNED DATA PRESENTATIONS

Data presentations planned to support writing the UX007G-CL201 CSR are listed in [Table 6](#).

Table 6: Planned Data Presentations

Output Type	Title
	Demographic Data
Table	Subject Disposition – Randomized Population
Table	Protocol Deviations – Efficacy Analysis Set
Table	Demographics – Efficacy Analysis Set
Table	Demographics by Age Group – Efficacy Analysis Set
Table	Glut1 DS Disease History – Efficacy Analysis Set
Table	Seizure History – Efficacy Analysis Set
Table	Study Drug Exposure – Efficacy Analysis Set
Table	Summary of Diet Diary Review – Efficacy Analysis Set
Table	Dosing Compliance – Days Dose Missed by Study Period – Efficacy Analysis Set
	Primary and Secondary Efficacy Analyses – Seizures
Table	Seizures – Week 8 Analysis – Summary – Efficacy Analysis Set
Table	Observable Seizures – Week 8 Analysis – Summary – Efficacy Analysis Set
Table	Absence Seizures – Week 8 Analysis – Summary – Efficacy Analysis Set
Table	Seizures – Reduction from Baseline – Week 8 Analysis – ANCOVA – Efficacy Analysis Set
Table	Observable Seizures – Reduction from Baseline – Week 8 Analysis – ANCOVA – Efficacy Analysis Set
Table	Absence Seizures – Reduction from Baseline – Week 8 Analysis – ANCOVA – Efficacy Analysis Set
Table	Seizure Response – Week 8 Analysis – Logistic Regression – Efficacy Analysis Set
Table	Observable Seizure Response – Week 8 Analysis – Logistic Regression – Efficacy Analysis Set
Table	Absence Seizure Response – Week 8 Analysis – Logistic Regression – Efficacy Analysis Set
	Additional Efficacy Analyses – Seizures
Table	Seizures – Week 8 Analysis – Summary – Per Protocol Analysis Set
Table	Observable Seizures – Week 8 Analysis – Summary – Per Protocol Analysis Set
Table	Absence Seizures – Week 8 Analysis – Summary – Per Protocol Analysis Set
Table	Seizures – Reduction from Baseline – Week 8 Analysis – ANCOVA – Per Protocol Analysis Set
Table	Observable Seizures – Reduction from Baseline – Week 8 Analysis – ANCOVA – Per Protocol Analysis Set
Table	Absence Seizures – Reduction from Baseline – Week 8 Analysis – ANCOVA – Per Protocol Analysis Set
Table	Seizure Response – Week 8 Analysis – Logistic Regression – Per Protocol Analysis Set
Table	Observable Seizure Response – Week 8 Analysis – Logistic Regression – Per Protocol Analysis Set
Table	Absence Seizure Response – Week 8 Analysis – Logistic Regression – Per Protocol Analysis Set

Output Type	Title

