APPENDIX A EFFICACY ENDPOINT SUMMARY TABLE

Test / Instrument	Eligible Study Population	Endpoint	Subjects Applicable	Endpoint Level	Timepoints for Assessments	Statistical Approach: Week 8 Analyses	Statistical Approach: Week 52 Analyses
Seizure Diary + EEG	Efficacy Analysis Set	Reduction from baseline in frequency of seizures	All	Primary	Diary: daily from Screening to 52/ET; EEG: Screening, Randomization, Week 8, 26, 31	ANCOVA	Estimation
Seizure Diary + EEG	Efficacy Analysis Set	Seizure response	All	Secondary	Diary: daily from Screening to 52/ET; EEG: Screening, Randomization, Week 8, 26, 31	Logistic Regression	Estimation
Seizure Diary	Efficacy Analysis Set – Observable Seizures	Reduction from baseline in frequency of observable seizures	All	Secondary	Daily from Screening to 52/ET	ANCOVA	Estimation
Seizure Diary	Efficacy Analysis Set – Observable Seizures	Observable seizure response	All	Secondary	Daily from Screening to 52/ET	Logistic Regression	Estimation
EEG	Efficacy Analysis Set – Absence Seizures	Reduction from baseline in frequency of absence seizures	All	Secondary	Screening, Randomization, Week 8, 26, 31	ANCOVA	Estimation
EEG	Efficacy Analysis Set – Absence Seizures	Absence seizure response	All	Secondary	Screening, Randomization, Week 8, 26, 31	Logistic Regression	Estimation
CANTAB	Efficacy Analysis Set	Change from baseline in CANTAB RTI Simple Choice Median Reaction Time (RTIMDSRT)	All	Secondary	Screening, Randomization, Week 4, 8, 26, 31, 36, 52, ET	GEE Linear	Estimation

Test / Instrument	Eligible Study Population	Endpoint	Subjects Applicable	Endpoint Level	Timepoints for Assessments	Statistical Approach: Week 8 Analyses	Statistical Approach: Week 52 Analyses
CANTAB	Efficacy Analysis Set	Change from baseline in CANTAB RTI Five Choice Median Reaction Time (RTIMDFRT)	All	Secondary	Screening, Randomization, Week 4, 8, 26, 31, 36, 52, ET	GEE Linear	Estimation
CANTAB	Efficacy Analysis Set	Change from baseline in CANTAB RTI Simple Choice Standard Deviation (RTISRSD)	All	Secondary	Screening, Randomization, Week 4, 8, 26, 31, 36, 52, ET	GEE Linear	Estimation
CANTAB	Efficacy Analysis Set	Change from baseline in CANTAB SSP Span Length (SSPSLF)	All	Secondary	Screening, Randomization, Week 4, 8, 26, 31, 36, 52, ET	GEE Linear	Estimation
CANTAB	Efficacy Analysis Set	Change from baseline in CANTAB PAL Total Errors (Adjusted) (PALTEA)	All	Secondary	Screening, Randomization, Week 4, 8, 26, 31, 36, 52, ET	GEE Linear	Estimation

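### The SAP gives two different analysis sets for the four type-specific seizure endpoints, and has no rule for response when the observed baseline is zero

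*SAP*

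**What the plan says.** SAP 6.3 defines the Efficacy Analysis Set as every randomized subject who took at least one dose, with no restriction by seizure type. SAP 8.6.4 uses that set for all four type-specific endpoints. For observable reduction it says "Reduction from baseline in frequency of observable seizures will be analyzed, based on the Efficacy Analysis Set, using linear regression"; for absence response it says "Absence seizure response at Week 8 will be analyzed, based on the Efficacy Analysis Set, using logistic regression"; observable response and absence reduction are worded the same way. The main model tables in Table 6 follow suit, for example "Observable Seizures – Reduction from Baseline – Week 8 Analysis – ANCOVA – Efficacy Analysis Set".

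Appendix A gives a different eligible population: "Efficacy Analysis Set – Observable Seizures" for the two diary endpoints, and the matching absence subset for the two EEG endpoints. SAP 5.6 says the classification by seizure type serves to "define which subjects are included in secondary endpoint analyses of specific seizure types".

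For the per-protocol versions, 8.6.4 calls for "the Per Protocol Analysis Set – Absence Seizures for endpoints involving seizures from EEG only", and for the diary counterpart in the same way. Each of these sets is built from a restricted set: 6.4.1 says it "is the subset of subjects in the Efficacy Analysis Set – Observable Seizures who met the following criteria" and 6.4.2 says it "is the subset of subjects in the Efficacy Analysis Set – Absence Seizures who met the following criteria".

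SAP 5.7.3 defines percent reduction with the baseline frequency as denominator, and 5.7.4 scores response from that quotient at a 50% threshold. SAP 7.1 imputes non-response only when data are completely missing.

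**The concern.** Two written rules give two estimates for the same named endpoint. Either could be called pre-specified afterwards, including after the data have been seen. Under the full-set rule, the estimate is averaged over subjects who had little or none of that seizure type to reduce. The responder analyses have a further problem: for some subjects the endpoint does not exist as defined, so a programmer would have to invent a rule.

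What is at stake is limited to secondary endpoints, which Protocol 7.6 tests without multiplicity adjustment, and to the additional fallback analysis in SAP 8.6.3. That section tests absence (H02) and observable (H03) reductions in what it calls subgroups, without naming their analysis sets.

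**Working it through.** **1. The plan's own figure.** The only stated figure is power for the overall endpoint (SAP 3.5): about 40 subjects, difference 50%, SD 55%, one-sided alpha 0.05, allocated 3:1 (SAP 3.3). With 30 vs 10, the standardized difference is 50 / (55 × √(1/30 + 1/10)) = 50 / 20.08 = 2.49, and 2.49 − 1.645 = 0.845. Power is 0.801 by the normal approximation and 0.788 by the noncentral t, so the stated 80% reproduces. No figure is given for the type-specific endpoints.

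**2. Does other text settle the set?**

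| SAP location | What it supports |
|---|---|
| 8.6.4 main analyses; Table 6 main titles | Full set |
| Appendix A; 5.6 | Subsets |
| 8.6.4 per-protocol wording, with 6.4.1 and 6.4.2 | Subsets |
| Table 6 per-protocol titles | Unrestricted Per Protocol Analysis Set |
| 8.6.6 | Repeats the analyses in the two subsets, for subjects with at least 80% compliance; fits a full-set main analysis |
| 7.1 | Names all three sets without assigning endpoints |
| 8.6.3 fallback (H02, H03) | No set named |
| Table 6, tables labelled Absence at Baseline | A set that Section 6 does not define |

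The evidence is split, and no sentence says which source governs.

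**3. Whom does the full set add?** This follows from the 5.6 definitions.
- Absence endpoints: any Randomization EEG frequency above 0 makes a subject an Absence Seizures Subject. Everyone outside that subset therefore has an EEG baseline of exactly 0, or no EEG.
- Observable endpoints: with both measures observed, a subject outside the subset has a diary frequency below 4 and an EEG frequency of at least 4. Some have a few diary seizures, as 6.3.4 acknowledges; others may have none.

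**4. Response at zero baseline.** Baseline 0 and Week 8 0 gives 100 × 0/0; baseline 0 and Week 8 4 gives 100 × (−4)/0. Both are undefined. The ln(frequency + 1) reductions do exist: 0 and ln 1 − ln 5 = −1.61. The gap arises in three places:
- the full set, for every added absence subject with an observed EEG;
- inside the absence subset, when entry is by diary codes M to P or the Screening EEG and the Randomization EEG shows zero;
- overall seizure response, when a subject enters the observable group by the second 5.6 route (both frequencies below 4) with zero diary seizures.

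**5. Size for the reduction endpoints.** The documents give neither the share outside each subset nor those subjects' Week 8 values, so both are assumed. Suppose the true reduction is 50% vs 0%, and a share q of each arm is at zero at both times. The log effect becomes about (1 − q) × ln 2, so the estimated reduction is 1 − 2^−(1−q): 42.6%, 38.4% and 34.0% at q = 20%, 30% and 40%. An ANCOVA simulation (30 vs 10, log SD = ln 2 × 55/50, 6,000 runs) agrees: 42.5%, 38.7% and 34.2%, against about 50% in the subset. Power at each share was within 1 point between the sets.

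A second simulation generated seizure counts (diary: baseline median 8 to 20 per 4 weeks; EEG: median 10 to 100 per 24 hours with 12-hour recordings):

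| Scenario | Full set at 20% / 30% / 40% outside | Subset | Power, full minus subset |
|---|---|---|---|
| Observable, all added subjects at zero | 39–40 / 34–37 / 30–32% | 45–48% | 0 to +2 points |
| Observable, half of them with a low nonzero count | 41–43 / 39–41 / 36–38% | 45–48% | +2 to +8 points |
| Absence, 24-hour scale (5.7.2) | 37–42 / 34–38 / 30–34% | 45–50% | −2 to +1 points |

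On the 4-week scale named in 4.2, the absence levels differ but the gap is similar: 7–8, 12–13 and 16–18 points.

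**6. Size for response.** Illustration at a 20% share: 12/24 vs 2/8 is 50% − 25% = 25 points. If zero-baseline subjects count as non-responders, it is 12/30 vs 2/10 = 40% − 20% = 20 points. In general the difference is 25 × (1 − q): 17.5 points at 30% and 15 at 40%.

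**The case against.** The strongest reply is that 8.6.4 is the operative text and Appendix A a loose summary. Appendix A lists the plain Efficacy Analysis Set for CANTAB, 6MWT and GMFM-88, where 8.6.4 uses dedicated subsets, and it assigns diary absence types to the observable set. The Table 6 model titles and the wording of 8.6.6 fit a full-set main analysis. On this view, correcting Appendix A and the sentence in 5.6 is as valid a repair as changing 8.6.4.

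That weakens any claim that the subsets are the only possible reading, and this much of it stands. It does not remove the conflict. SAP 8.6 presents Appendix A as the more thorough table, and 5.6 states a purpose for the classification that a full-set analysis of these endpoints leaves unfulfilled. The entry All under Subjects Applicable in Appendix A does not help either: that column contrasts with select sites and age limits, not with seizure type.

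A reader might also infer that the per-protocol sets settle the matter for the subsets. They do not, because the Table 6 per-protocol titles are unrestricted. Nor do the Table 6 figures prove a contradiction: the full-set and subset figures are largely different displays, compatible with a full-set main analysis plus descriptive subset plots.

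**Conclusion.** The conflict over the analysis set is real and unresolved in the text, and response is undefined at an observed zero baseline. Both should be fixed before unblinding. With 20% to 40% of subjects outside a subset, and most of those added at zero at baseline and Week 8, the full-set reduction estimate is roughly 5 to 18 points smaller than the subset estimate. These sizes are illustrative. In particular, 5.6 fixes only the baseline of the added absence subjects; nothing says their Week 8 EEG is also zero.

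Three stronger readings are not supported:
- That the primary result is at risk. SAP 8.6.3 names the Efficacy Analysis Set for the primary analysis without conflict.
- That the full set costs power. The simulated change is small in most scenarios, and for observable seizures it can favour the full set.
- That the full-set reduction models cannot be run. The ln(frequency + 1) models are defined at zero; only the response endpoints are not.

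**What to change.** Before unblinding:
1. Name one main analysis set for each type-specific endpoint, identically in 8.6.4, Table 6 (including the per-protocol titles) and Appendix A, and name the sets for H02 and H03 in 8.6.3. The 5.6 subsets fit the stated purpose of the classification, with the full-set reduction analysis kept as supportive. If the sponsor keeps the full set as main, amend 5.6 and Appendix A and report the subset analysis alongside.
2. State how an observed zero baseline is handled in each response endpoint, for example as non-response in overall response and as exclusion from type-specific response, and report the number of such subjects by arm. Choosing the subsets does not make this rule unnecessary.
3. Define Absence at Baseline if those Table 6 tables are kept, or drop them if they would duplicate the main absence tables.

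The cost is SAP wording and table titles. If the subsets become the main sets, the type-specific tables shrink (from 40 subjects to 32, 28 or 24 at the assumed shares). Observable seizures may lose a few points of power, up to about 8 in the scenario where half of the excluded subjects have some diary seizures. With exclusion under item 2, reduction and response would rest on slightly different subjects, which the counts by arm would make visible.

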8.6.5 Exploratory Efficacy Endpoints

Summary statistics, including p-values for differences between treatment groups during the double-blind placebo-controlled treatment period, will be provided by visit for the following exploratory endpoints over the entire study period by treatment group and overall: specific seizure types derived from seizure diary, specific seizure types derived from EEG, CNS, CGI-I, SF-10 and SF-12 v2.

A data listing will be provided for the following exploratory endpoints available at select sites over the entire study period: PPVT, PEDI-CAT, Gait analysis during 6-minute walk test (6MWT), GMFM-88 domains (lying/rolling, sitting, crawling/kneeling, standing, and walking/running/jumping), Beery-VMI and RCPM.

8.6.6 Subset Analyses of Primary and Select Secondary Endpoints

Analyses of primary and secondary endpoints involving seizures will be repeated for the following subgroups: Efficacy Analysis Set – Observable Seizures and Efficacy Analysis Set – Absence Seizures, for the subjects with $\geq 80\%$ dosing compliance from baseline to week 8 (see Section 8.5.4).

8.7 Safety Analyses

All safety analyses will be based on the Safety Analysis Set. In general safety analyses will be completed using summary statistics, graphs or subject listings. No planned inferential testing of safety endpoints is planned. If after the planned analysis it is determined by the medical writer and study medical monitor that inferential tests of significance may help to provide context for safety information these tests may be performed and identified in the CSR. Summaries will be done by study period and overall.

Analyses and summaries will be performed by study period, by treatment group, for subjects while taking UX007, and overall.

